10.1 Definitions

10.1.1 Adverse Events (AEs)

Definition: any unfavorable medical occurrence in a human subject including any abnormal sign, symptom, or disease.

Grading: the descriptions and grading scales found in the revised NCI Common Terminology Criteria for Adverse Events (CTCAE) version 4.0 will be utilized for all toxicity reporting. A copy of the CTCAE version 4.0 can be downloaded from the CTEP web site: <http://ctep.cancer.gov/reporting/ctc.html>. Grade 1-2 events will be recorded for the first fifty enrolled patients. Subsequently, only events graded as 3 or greater will be recorded. Fifty patients should be sufficient to estimate the true incidence of any adverse event to within $\pm 14\%$ with 95% confidence intervals.

Attribution (relatedness), Expectedness, and Seriousness: the definitions for the terms listed that should be used are those provided by the Department of Health and Human Services' Office for Human Research Protections (OHRP). A copy of this guidance can be found on OHRP's website: (<http://www.hhs.gov/ohrp/policy/AdvEvtGuid.htm>).

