10.1.2 Serious Adverse Event (SAE)

Definition: any adverse drug experience occurring at any dose that results in any of the following outcomes:

- Death
- A life-threatening adverse drug experience
- Inpatient hospitalization or prolongation of existing hospitalization
- A persistent or significant disability/incapacity (i.e., a substantial disruption of a person's ability to conduct normal life functions)
- A congenital anomaly/birth defect

- Any other experience which, based upon appropriate medical judgment, may jeopardize the subject and may require medical or surgical intervention to prevent one of the outcomes listed above

All unexpected SAEs must be reported to the FDA.

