10.6 Reporting to the FDA

The conduct of the study will comply with all FDA safety reporting requirements. **PLEASE NOTE THAT REPORTING REQUIREMENTS FOR THE FDA DIFFER FROM REPORTING REQUIREMENTS FOR HRPO/QASMC.** It is the responsibility of the Washington University principal investigator to report any unanticipated problem to the FDA as follows:

- Report any unexpected fatal or life-threatening adverse experiences (Section 10.1.4) associated with use of the drug by telephone or fax no later than **7 calendar days** after initial receipt of the information.
- Report any serious, unexpected adverse experiences (Section 10.1.2), as well as results from animal studies that suggest significant clinical risk within **15 calendar days** after initial receipt of this information.

All MedWatch forms will be sent by the investigator or investigator's team to the FDA at the following address or by fax:

Food and Drug Administration

Center for Drug Evaluation and Research
Division of Oncology Drug Products
[name]
[name]
FAX: [name]

Secondary sites must submit a completed MedWatch form to the Washington University PI and research coordinator within **4 calendar days** (for fatal or life-threatening adverse experiences) or **11 calendar days** (for serious, unexpected adverse experiences). The Washington University PI will be responsible for submitting all MedWatch forms from secondary sites to the FDA within the timeframes specified above.

10.7 Timeframe for Tracking Reportable Events:

Adverse events will be tracked for 30 days following the last day of study treatment, or until the start of a new chemotherapy/treatment, whichever comes first.

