11.0 DATA SAFETY MONITORING PLAN

In compliance with the Washington University Institutional Data and Safety Monitoring Plan, the Data and Safety Monitoring Committee (DSMC) will meet to review toxicity data at least every 6 months following the activation of the first secondary site. The report will be prepared by the statistician and will be submitted to the Quality Assurance and Safety Monitoring Committee (QASMC). This report will include:

- HRPO protocol number, protocol title, Principal Investigator name, data coordinator name, regulatory coordinator name, and statistician
- Date of initial HRPO approval, date of most recent consent HRPO approval/revision, date of HRPO expiration, date of most recent QA audit, study status, and phase of study
- History of study including summary of substantive amendments; summary of accrual suspensions including start/stop dates and reason; and summary of protocol exceptions, error, or breach of confidentiality including start/stop dates and reason
- Study-wide target accrual and study-wide actual accrual including numbers from participating sites
- Protocol activation date at each participating site
- Average rate of accrual observed in year 1, year 2, and subsequent years at each participating site
- Expected accrual end date and accrual by site
- Objectives of protocol with supporting data and list the number of participants who have met each objective
- Measures of efficacy
- Early stopping rules with supporting data and list the number of participants who have met the early stopping rules
- Summary of toxicities at all participating sites
- Abstract submissions/publications
- Summary of any recent literature that may affect the safety or ethics of the study

Until such a time as the first secondary site activates this protocol, a semi-annual DSM report to be prepared by the study team will be submitted to the QASM Committee beginning 6 months after study activation at Washington University.

The study principal investigator and Research Patient Coordinator will monitor for serious toxicities on an ongoing basis. Once the principal investigator or Research Patient Coordinator becomes aware of an adverse event, the AE will be reported to the HRPO and QASMC according to institutional guidelines.

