A power analysis was performed using Chi-square test for the association between mutation and response to decitabine. The frequency of *DNMT3A*, *IDH1/2*, and *TET2* mutations in AML and MDS patients are each between 15% and 30% in multiple cohorts.[29-37] **Table 3** shows the minimal detectable differences of response rates between mutant and wild-type cases, assuming an expected overall 45% CR/CRi rate and 80% power. For an average of 20% frequency of a mutated gene, for example, 100 patients will provide 80% power to detect 30% difference at a 2-sided 0.1 alpha error. The purpose of this study is to determine whether any of these mutations result in a clinically significant association that would warrant pre-treatment testing. We believe that a reasonable cut off would be if at least 30% of clinical response could be attributed to the presence of a specific mutation. However, we anticipate that more power could be achieved as we assess patient groups with combined characteristics (e.g. *DNMT3A* mutation or loss of *DNMT3A* expression). In addition, we expect that the majority of the enrolled 125 patients can be used in the analysis (since all of our molecular information will be acquired within 30 days of enrollment, we anticipate a drop-out rate of 20% or less).

Table 3. Detectable mutation associated response rates (80% power, $\alpha = 0.05$)

Total N	% of patients with a given mutation	Detectable response difference	Sensitivity of mutation to predict response at minimum detectable response difference*
100	15%	0.40	80%
	20%	0.35	75%
	30%	0.30	67%
	40%	0.27	61%
	50%	0.26	58%

* Assuming the overall response rate (CR/CRi) of 45%

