14.3 Sample Size

We anticipate initially enrolling 25 patients at Washington University. Once we establish a routine exome analysis with validation and calculation of the rate of patient-specific mutation clearance, we will enroll an additional 100 patients from at least 2 additional centers.

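### After patient 50 the adverse-event recording rule makes no exception for serious events, so, read as written, expected serious grade 1-2 events are not recorded in up to 75 of 125 planned patients

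*Combined protocol and SAP*

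**What the plan says.** Section 10.1.1 sets the recording rule in two sentences: "Grade 1-2 events will be recorded for the first fifty enrolled patients", and then "Subsequently, only events graded as 3 or greater will be recorded". It supports the cut-off by saying that fifty patients estimate the incidence of any adverse event to within 14 percentage points at 95% confidence. No exception for serious events is stated. The same rule stands in all five protocol versions in the file (numbered 10.1 in the two that use the older numbering of Section 10).

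Section 10.1.2 defines a serious adverse event by its outcome. One listed outcome is "Inpatient hospitalization or prolongation of existing hospitalization". No grade appears in the definition.

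Section 10.6 requires the lead investigator to "Report any serious, unexpected adverse experiences" to the FDA, again with no grade limit. Section 11.0 requires the monitoring report to include a "Summary of toxicities at all participating sites". Section 14.2.4 plans one set of adverse-event summaries (number and percent of patients, by attribution, grade and cycle) and names no separate table of serious events. Section 15.0 makes the adverse-event form due whenever an adverse event occurs, whatever its grade.

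**The concern.** Grade and seriousness are different scales. Grade describes the severity of an event; seriousness, as Section 10.1.2 defines it, describes what the event led to. A recording threshold on grade alone can therefore drop events that the same protocol calls serious. An example is an expected event graded 2 that leads to an admission in patient 51 or later.

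At stake is the completeness of the safety record for most of the trial. If these events are not recorded, the committee reviewing toxicity does not see them, and the final tables count the affected patients as free of the event. Sites also hold instructions that cannot all be followed: do not record the event (10.1.1), complete a form for every adverse event (15.0) and, if the event is serious and unexpected, report it to the FDA (10.6).

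**Working it through.** **1. The plan's own figure.** The 95% half-width for a proportion is 1.96 × √(p(1−p)/n). At the worst case p = 0.5 with n = 50 this is 1.96 × √(0.25/50) = 0.1386, or 14 points after rounding. The stated precision is reproduced. It speaks to how precisely the incidence of an adverse event is estimated; it gives no reason to stop recording serious events.

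**2. Patients under the reduced rule.** Section 14.3 states "We anticipate initially enrolling 25 patients at Washington University" and then "we will enroll an additional 100 patients from at least 2 additional centers". So 25 + 100 = 125, which matches Section 14.2.2 ("we expect that the majority of the enrolled 125 patients can be used in the analysis"). Then 125 − 50 = 75, and 75/125 = 60%. Because 50 exceeds 25, all 75 fall in the second stage, when the additional centers enroll.

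**3. Where else a serious grade 1-2 event after patient 50 could be captured.**
- FDA (10.1.2, 10.1.3, 10.6): serious events that are unexpected. Expected ones are outside.
- HRPO (10.1.5, 10.2): unanticipated problems, which must be unexpected by definition.
- QASMC (10.3): only unanticipated problems that HRPO has acknowledged as reportable.
- Secondary sites (10.4): reportable events as described in a Section 7.6. The table of contents lists only 7.1, 7.1.1 and 7.1.2 under Section 7, so the trigger is unclear.
- Section 11.0: adverse events go to HRPO and QASMC under institutional guidelines that are not in the documents.
- Section 13.0: documentation concerning SAE reports is kept on file, but the section does not say which events generate a report.
- Section 15.0: a form for any adverse event. This contradicts 10.1.1 and does not say that it overrides it.

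None of these clearly captures an expected serious event of grade 1 or 2. An unexpected one has a reporting route, but 10.1.1 keeps it out of the adverse-event record.

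**4. Effect on the summaries.** Section 14.1 defines the safety population as every dosed patient. If the events are recorded only in the first 50 but the percentage is taken over 125, a true rate r appears on average as 50r/125 = 0.4r.

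**5. Illustration only.** The documents give no rate for expected serious grade 1-2 events. Let r be the assumed proportion of patients with at least one such event, equal before and after patient 50, with full accrual and all 125 patients dosed.

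| Assumed r | Patients missed, 75r | Chance of missing at least one, 1 − (1 − r)^75 | Pooled rate shown, 0.4r |
|---|---|---|---|
| 1% | 0.75 | 53% | 0.4% |
| 2% | 1.5 | 78% | 0.8% |
| 5% | 3.75 | 98% | 2% |
| 10% | 7.5 | >99.9% | 4% |

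**6. What full recording would give.** With serious events recorded in all 125 patients, the worst-case half-width is 1.96 × √(0.25/125) = 0.0877, or 8.8 points against 13.9. If none of a given kind is seen, the one-sided 95% upper bound is 1 − 0.05^(1/125) = 2.4%, against 1 − 0.05^(1/50) = 5.8%.

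**The case against.** The strongest reply is that this is an inconsistency between sections and not a demonstrated loss. Section 15.0 asks for a form at every adverse event, Section 11.0 sends adverse events to HRPO and QASMC without a grade limit, and Section 13.0 foresees SAE reports on file. Sites may well record every serious event in practice. This stands to the extent that loss cannot be asserted as certain. It does not remove the defect: none of these sections expressly overrides the rule in 10.1.1, and a protocol should not depend on sites disregarding its text.

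A reader might infer that all serious grade 1-2 events disappear after patient 50. The documents do not support that. Unexpected serious events must reach the FDA whatever their grade, and those that are unanticipated problems must also reach HRPO.

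A reader might also infer that low-grade events leading to a dose hold or to stopping treatment are lost. That does not hold either. Reasons for stopping are documented in the case report forms (5.3) and summarized (14.2.1). Section 15.0 has a form for dose modifications and one for laboratory results, and 14.2.4 summarizes laboratory grades separately. The laboratory hold limits in 6.2 cannot be shown to lie below grade 3, because the CTCAE cut-points are not in the documents.

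Finally, whether an event that leads to admission would be graded 1 or 2 depends on CTCAE v4.0, which the protocol cites but does not reproduce. That is a fair caution about frequency. Nothing in 10.1.2 excludes such events.

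**Conclusion.** The point holds for expected serious events of grade 1 or 2. Under 10.1.1 as written they are not recorded after patient 50, in up to 75 of 125 planned patients (60%), and they would be missing from the 14.2.4 summaries and the Section 11 toxicity summary. For unexpected serious events the finding is narrower: a conflict between 10.1.1 and 10.6. For every grade 1-2 event after patient 50 there is also a conflict between 10.1.1 and 15.0.

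This rests on three assumptions: enrolment reaches 125; sites follow 10.1.1 literally where it conflicts with 15.0; and some expected serious events are graded below 3. The number of events cannot be derived from the documents, so the rates in the table above are not an estimate of the loss. The point should be corrected because a stated rule weakens the safety record and the correction is cheap.

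**What to change.** In Section 10.1.1, keep the grade threshold for non-serious events and add one clause: "Subsequently, only events graded as 3 or greater will be recorded", together with all serious adverse events regardless of grade. Align the adverse-event form entry in Section 15.0 with that rule so that sites have one instruction. In Section 14.2.4 and in the Section 11 report, summarize serious adverse events on the full safety population, separately from the all-grade tables.

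The cost is a few extra adverse-event entries and one more summary. Sites must already judge seriousness to meet the FDA reporting duty. The change concerns data capture only. If the sponsor already intends to record every serious event, it simply puts that intention into the text.

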10.1.2 Serious Adverse Event (SAE)

Definition: any adverse drug experience occurring at any dose that results in any of the following outcomes:

- Death
- A life-threatening adverse drug experience
- Inpatient hospitalization or prolongation of existing hospitalization
- A persistent or significant disability/incapacity (i.e., a substantial disruption of a person's ability to conduct normal life functions)
- A congenital anomaly/birth defect

- Any other experience which, based upon appropriate medical judgment, may jeopardize the subject and may require medical or surgical intervention to prevent one of the outcomes listed above

All unexpected SAEs must be reported to the FDA.

10.1.3 Unexpected Adverse Experience

Definition: any adverse drug experience, the specificity or severity of which is not consistent with the current investigator brochure (or risk information, if an IB is not required or available).

Events that are both serious AND unexpected must be reported to the FDA.

10.1.4 Life-Threatening Adverse Experience

Definition: any adverse drug experience that places the subject (in the view of the investigator) at immediate risk of death from the reaction as it occurred, i.e., it does not include a reaction that, had it occurred in a more severe form, might have caused death.

Life-threatening adverse experiences must be reported to the FDA.

10.1.5 Unanticipated Problems

Definition:

- unexpected (in terms of nature, severity, or frequency) given (a) the research procedures that are described in the protocol-related documents, such as the IRB-approved research protocol and informed consent document; and (b) the characteristics of the subject population being studied;
- related or possibly related to participation in the research (in this guidance document, possibly related means there is a reasonable possibility that the incident, experience, or outcome may have been caused by the procedures involved in the research); and
- suggests that the research places subjects or others at a greater risk of harm (including physical, psychological, economic, or social harm) than was previously known or recognized.

10.1.6 Noncompliance

Definition: failure to follow any applicable regulation or institutional policies that govern human subjects research or failure to follow the determinations of the IRB. Noncompliance may occur due to lack of knowledge or due to deliberate choice to ignore regulations, institutional policies, or determinations of the IRB.

10.1.7 Serious Noncompliance

Definition: noncompliance that materially increases risks, that results in substantial harm to subjects or others, or that materially compromises the rights or welfare of participants.

10.1.8 Protocol Exceptions

Definition: A planned deviation from the approved protocol that are under the research team's control. Exceptions apply only to a single participant or a singular situation.

Local IRB Pre-approval of all protocol exceptions must be obtained prior to the event. For secondary sites, the Washington University PI will issue approval of the exception, but it must also be submitted to the local IRB with documentation of approval forwarded to Washington University. Washington University IRB approval is not required for protocol exceptions occurring at secondary sites.

10.2 Reporting to the Human Research Protection Office (HRPO) at Washington University:

The PI is required to promptly notify the IRB of the following events:

- Any unanticipated problems involving risks to participants or others which occur at WU, any BJH or SLCH institution, or that impacts participants or the conduct of the study.
- Noncompliance with federal regulations or the requirements or determinations of the IRB.
- Receipt of new information that may impact the willingness of participants to participate or continue participation in the research study.

These events must be reported to the IRB within **10 working days** of the occurrence of the event or notification to the PI of the event. The death of a research participant that qualifies as a reportable event should be reported within **1 working day** of the occurrence of the event or notification to the PI of the event.

10.3 Reporting to the Quality Assurance and Safety Monitoring Committee (QASMC) at Washington University

The PI is required to notify the QASMC of any unanticipated problem occurring at WU or any BJH or SLCH institution that has been reported to and acknowledged by HRPO as reportable. (Unanticipated problems reported to HRPO and withdrawn during the review process need not be reported to QASMC.)

QASMC must be notified within **10 days** of receipt of IRB acknowledgment via email to a QASMC auditor.

10.4 Reporting Requirements for Secondary Sites

The research team at each secondary site is required to promptly notify the Washington University PI and research coordinator of all reportable events (as described in Section 7.6) within **1 working day** of the occurrence of the event or notification of the secondary site's PI of the event. This notification may take place via email if there is not yet enough information for a formal written report (using either an FDA MedWatch form if required or an institutional SAE reporting form if not). A formal written report must be sent to the Washington University PI and research coordinator within **10 working days** of the occurrence of the event or notification of the secondary site's PI of the event. The death of a research participant that qualifies as a reportable event should be reported within **1 working day** of the occurrence of the event or notification of the secondary site's PI of the event.

The research team at a secondary site is responsible for following its site's guidelines for reporting applicable events to its site's IRB according to its own institutional guidelines. The research team at Washington University is responsible for reporting all applicable events to the FDA.

10.5 Reporting to Secondary Sites

The Washington University PI (or designee) will notify the research team at each secondary site of all reportable events that have occurred at other sites within **10 working days** of the occurrence of the event or notification of the PI of the event. This includes events that take place both at Washington University and at other secondary sites, if applicable.

10.6 Reporting to the FDA

The conduct of the study will comply with all FDA safety reporting requirements. **PLEASE NOTE THAT REPORTING REQUIREMENTS FOR THE FDA DIFFER FROM REPORTING REQUIREMENTS FOR HRPO/QASMC.** It is the responsibility of the Washington University principal investigator to report any unanticipated problem to the FDA as follows:

- Report any unexpected fatal or life-threatening adverse experiences (Section 10.1.4) associated with use of the drug by telephone or fax no later than **7 calendar days** after initial receipt of the information.
- Report any serious, unexpected adverse experiences (Section 10.1.2), as well as results from animal studies that suggest significant clinical risk within **15 calendar days** after initial receipt of this information.

All MedWatch forms will be sent by the investigator or investigator's team to the FDA at the following address or by fax:

Food and Drug Administration

Center for Drug Evaluation and Research
Division of Oncology Drug Products
[name]
[name]
FAX: [name]

Secondary sites must submit a completed MedWatch form to the Washington University PI and research coordinator within **4 calendar days** (for fatal or life-threatening adverse experiences) or **11 calendar days** (for serious, unexpected adverse experiences). The Washington University PI will be responsible for submitting all MedWatch forms from secondary sites to the FDA within the timeframes specified above.

10.7 Timeframe for Tracking Reportable Events:

Adverse events will be tracked for 30 days following the last day of study treatment, or until the start of a new chemotherapy/treatment, whichever comes first.

